3.4.2 Efficacy assessments

3.4.2.1 Response Definitions

Standard anatomic MRI in conjunction with clinical evaluation such as neurologic status and corticosteroid use, remains the key determinant of response to therapy and the evaluation of tumor recurrence for low grade glioma. Increase in contrast enhancement, worsening cerebral edema, and mass effect are traits of malignant transformation. Acquiring tissue samples to confirm tumor upgrade, although considered the “gold standard” for determining the presence of viable tumor, can result in both false positives and negatives that relate to sampling error. Evaluating response in low-grade glioma by radiographic imaging is an accepted means of determining response and is the standard by which NIH grant-funded brain tumor consortiums operate.

One of the secondary endpoints will be response rate, based on the best response achieved (see below for definition of best response). In order to ensure comparability of data from this trial with data from earlier trials, this trial will retain the traditional evaluation definition as the primary way to define response. Response will be determined by the bi-dimensional diameters. However, RECIST criteria will be collected and used for secondary evaluation.

Definitions of Response

Measurable Disease: Bidimensionally measurable lesions with clearly defined margins by MRI scan. A measurable lesion must be 1 mm or larger in longest diameter.

Evaluable Disease: Unidimensionally measurable lesions, masses with margins not clearly defined.

Objective Status, To Be Recorded at Each Evaluation: If there are too many lesions to measure at each evaluation, choose the largest two to be followed before a patient is entered on study. The remaining lesions will be considered evaluable for the purpose of objective status determination. Unless progression is observed, objective status can only be determined when ALL measurable and evaluable sites and lesions are assessed.

Complete Response (CR): Complete disappearance of all measurable and evaluable disease. No new lesions. No evidence of non-evaluable disease. All measurable, evaluable and non-evaluable lesions and sites must be assessed using the same techniques as baseline. Patients must be on minimal or no steroids.

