Partial Response (PR): Greater than or equal to 50% decrease under baseline in the sum of products of perpendicular diameters of all measurable lesions. No progression of evaluable disease. No new lesions. All measurable and evaluable lesions and sites must be assessed using the same techniques as baseline. Responders must be on the same or decreasing doses of dexamethasone.

Partial Response, Non-Measurable (PRNM): Not applicable.

Stable / No Response (NR) / No Change (NC): Does not qualify for CR, PR, or progression. The designation of Stable/No Response requires a minimum of 8 weeks duration. All measurable and evaluable sites must be assessed using the same techniques as baseline.

Progression: 25% increase in the sum of products of all measurable lesions over smallest sum observed (over baseline if no decrease) using the same techniques as baseline, OR clear worsening of any evaluable disease, OR appearance of any new lesion/site, OR failure to return for evaluation due to death or deteriorating condition (unless clearly unrelated to this cancer).

Unknown: Progression has not been documented and one or more measurable or evaluable sites have not been assessed.

Best Response: This will be calculated from the sequence of objective statuses.

For patients with all disease sites assessed every evaluation period, the best response will be defined as the best objective status as measured according to the previously noted definitions. Best response is unknown if all objective status determinations before progression are unknown.

Neurological Exam: Although not used for determining response, it is useful to evaluate improvement in the neurologic exam that should coincide with objective measurement of tumor size.

+2 Definitely better
+1 Possibly better
0 Unchanged
-1 Possibly worse
-2 Definitely worse
(compared to baseline)

Time to Death: From date of registration to date of death due to any cause.

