6.1.2. Endpoint Definitions and Sample Size

The following definitions will be used for statistical analysis:

- Response: Response is based on the best response. The best response is defined as the best objective status as measured by the sum of products of perpendicular diameters of all measurable lesions.
- Progression-free survival: Number of days from the day the patient was enrolled to the day the patient experiences an event of disease progression or recurrence or to the date of death if disease progression or recurrence is not reached. All events of disease progression or recurrence will be included, regardless of whether the event

occurred while the patient was still taking drug or had previously discontinued study drug. All events of death will be included for patients who had not experienced disease progression or recurrence. If the patient does not have an event of disease progression or recurrence nor as the patient died, the patient's data will be censored at the date of last contact with the patient.

- Overall survival: Number of days from the day the patient was enrolled until the date of death. If the patient is lost to follow-up, the patient's data will be censored at the date of last contact with the patient.

For this single-arm phase II trial, the primary endpoint will be 6-month progression-free survival (PFS-6). Patients will be analyzed based on intention to treat. The primary determination of treatment success will be based on the results for those patients who are shown to still be low-grade. The intent is to perform the primary analysis at the time the 6 month PFS is known for all patients.

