6.1.4 Analyses Time-points and planned analysis

Primary end-point – 6-month PFS:

Analyses will be performed after all enrolled patients have completed 6 months on study drug, or whenever the progression status of all patients has been established, whichever comes first. The primary analysis will be based on Kaplan-Meier method. Kaplan-Meier estimates and the associated 95% CIs will be calculated for the 6-month PFS separately for low-grade glioma patients and secondary malignant glioma patients. The Cox proportional hazards model will also be used to allow for adjustment of the prognostic factors including age, KPS, extent of resection, and number of prior chemotherapy regimens.

Secondary end-point – overall survival and objective response rate:

The method described above for the analysis of PFS-6 will be applied to the analysis of OS. Response is based on the best response, defined as the best objective status as measured by the sum of products of perpendicular diameters of all measurable lesions. The point estimate and the associated 2-sided 95% CI for the response rate will be calculated separately for low grade and secondary malignant tumors.

Secondary end-point – biologic correlates:

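### CR and PR count as best response on a single MRI with no confirming scan, so the response rate leans upward by an amount the plan cannot show; a confirmed rate should be reported beside it.

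*Combined protocol and SAP*

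**What the plan says.** Section 3.4.2.1 defines PR by "Greater than or equal to 50% decrease under baseline in the sum of products of perpendicular diameters of all measurable lesions", with no new lesions, no progression of evaluable disease and a steroid condition. CR is "Complete disappearance of all measurable and evaluable disease", also with conditions but no duration. On best response it says "This will be calculated from the sequence of objective statuses" and, for patients with all sites assessed each time, "the best response will be defined as the best objective status as measured according to the previously noted definitions". Section 6.1.2 repeats the rule ("The best response is defined as the best objective status as measured by the sum of products of perpendicular diameters of all measurable lesions"), as does section 6.1.4 ("Response is based on the best response, defined as the best objective status as measured by the sum of products of perpendicular diameters"). None of these asks for a second qualifying scan.

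Only stable disease carries a time rule: "The designation of Stable/No Response requires a minimum of 8 weeks duration". Progression is "25% increase in the sum of products of all measurable lesions over smallest sum observed", among other criteria.

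Section 3.4.1.2 schedules an MRI every 2 months for 12 months and then every 3 months for 12 months: 12/2 = 6 scans in year 1 and 12/3 = 4 in year 2. Section 3.4.2.3 has a neuro-oncologist review every objective response, comparing the latest image with the previous one, and a second neuro-oncologist adjudicate measurement discrepancies. Section 3.4.2.1 keeps the traditional bidimensional definition for comparability with earlier trials and collects RECIST for secondary evaluation.

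**The concern.** Best response takes the most favourable of several noisy readings against one noisy baseline. A tumour that has shrunk by less than half, or not at all, can cross the PR line once by error and is then a responder for good. Patients with more scans have more chances.

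Objective response rate is a secondary endpoint of a single-arm trial, so no control group carries the same excess. Response is also the outcome of the Cochran-Mantel-Haenszel and logistic analyses of p-Akt in section 6.1.4, repeated for PTEN methylation. The resulting odds ratio is meant to inform whether future studies should test p-Akt first.

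The documents make measurement error a fair worry. Section 3.4.2.1 lets a lesion count as measurable from 1 mm, section 1.1.3.4 describes these tumours as diffuse, and section 3.2.2.4 puts entry within 4 months of surgery. They give no figure for the error.

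**Working it through.** **The plan's own figure.** The plan states no expected response rate and no power for the marker analyses. Its one related figure is the primary power: 12 or more of 40 at 17% versus 40% gives exact one-sided alpha 0.030 and power 92.9%, so the stated figure of over 90% reproduces. It does not involve response.

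**Model.** From the plan: PR at a ratio to baseline of 0.5 or less; follow-up ends at a measured 25% rise over the smallest sum; 6 scans in year 1. Assumed: the log of the sum of products has independent normal error with SD s at baseline and at each scan, and the true shrinkage d is steady.

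One scan: P(false PR) = Φ{[ln 0.5 − ln(1 − d)] / (s√2)}. With d = 0 and s = 0.20 this is Φ(−0.693/0.283) = Φ(−2.45) = 0.7%. Repeated scans were simulated. For an unchanged tumour at s = 0.20 the figure rises to 1.8% over 3 scans and 2.4% over 6.

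**Forty patients, none a true responder.** Assumed mix: 20 unchanged, 10 at −20%, 10 at −30%. True progression was added as a constant hazard, independent of shrinkage, matched to the plan's PFS-6. At 8-week scans the chance of passing each interval is 0.40^(8/26) = 0.75 or 0.17^(8/26) = 0.58. The mean number of progression-free year-1 scans is the sum of its powers 1 to 6, about 2.5 or 1.3.

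| SD | Unchanged tumour, 6 scans: false PR | Mix, 6 scans, no true progression: false PRs, planned → confirmed | Mix, PFS-6 17% to 40%: false PRs, planned |
|---|---|---|---|
| 0.10 | 0.0% | 0.4 → 0.04 | 0.1-0.2 |
| 0.15 | 0.2% | 2.3 → 0.4 | 0.7-1.2 |
| 0.20 | 2.4% | 4.8 → 1.2 | 1.7-2.7 |
| 0.25 | 7% | 7.5 → 2.2 | 2.8-4.4 |

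Confirmed means PR on two consecutive scans. It cuts the last column to about 1 or fewer at every SD. At SD 0.20, 1.7-2.7 of 40 is an apparent response rate of 4% to 7% where the truth is 0.

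**Marker analyses.** With false-response probability f among true non-responders in both marker groups, the observed rate is p + (1 − p)f. Assume true rates of 30% and 10%. At f = 0.05 these become 33.5% and 14.5%, and the odds ratio falls from 3.86 to (0.335/0.665)/(0.145/0.855) = 2.97. At f = 0.10 it is 2.50. Simulated power (20 v 20 low-grade, 15 v 5 high-grade, two-sided 0.05 assumed) falls from 45% to 37% and 31%. With no marker effect the rejection rate stays just under 5%.

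**What confirmation costs.** A scan can still be a PR and also meet the progression rule: at 35% of baseline then 45%, the rise is 45/35 = 1.29. At SD 0.20 and 6 scans, detection of a true 60% shrinkage is 96% on the planned rule. With confirmation it is 80% if such a scan confirms and 66% if it does not. For a true 70% shrinkage the confirmed figures are 97% and 77%.

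**The case against.** The strongest reply is that the definition is deliberate and the stakes are modest. Section 3.4.2.1 keeps the traditional definition for comparability, every response is reviewed and discrepancies adjudicated, and the response rate is reported only as an estimate with a confidence interval, with no decision threshold. For unchanged tumours the excess is negligible at SD 0.15 or below. Confirmation also loses true responders. All of this stands, and it is why the planned rate should stay. It does not supply what is missing: review and adjudication control how a scan is read, not whether the shrinkage persists.

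Four stronger readings are tempting and not supported.

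- A reader might infer a false response rate near 12% (4.8 of 40 at SD 0.20). That needs all six scans to be available apart from noise-driven exits. At the plan's own PFS-6 of 17% to 40%, few patients have six progression-free scans.
- Section 1.5 might be read as predicting shrinkage of 20% to 40%. It says only that such agents may produce stability rather than regression, so the mix above is an assumption.
- The 8-week rule for stable disease might look like a confirmation demanded of stable disease and not of response. The first scheduled MRI falls at about 8 weeks, so it is a minimum duration and not a second-scan requirement.
- False responders might be thought to create marker associations. If unrelated to marker status, they only dilute real ones.

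**Conclusion.** The gap is real and its direction is clear: with no confirming scan, best-of-several response leans upward. The lean is small if measurement error is small: about 1 false PR in 40 or fewer at SD 0.15 or below. At SD 0.20 to 0.25 it is about 2 to 4 in 40. These counts rest on the assumed SD, patient mix, independent errors and constant progression hazard; the documents give none of these beyond the PFS-6 values. The consequences are confined to the response rate and the marker analyses of response. PFS-6 and its sample size are untouched.

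A reader might go on to conclude that confirmed response should replace the planned endpoint. The figures do not support that: at SD 0.20 it would miss 20% to 34% of true 60% responders, exchanging an upward bias for a downward one. Reporting both shows how much of the response rate persists. This is a cheap improvement and not a flaw that threatens the trial.

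**What to change.** In sections 3.4.2.1, 6.1.2 and 6.1.4:

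1. Keep the planned best-response definition for comparability with earlier trials.
2. Add a confirmed response rate, counting a CR or PR only if it is still met at the next scheduled MRI, with its two-sided 95% CI by grade.
3. Repeat the p-Akt and PTEN response analyses on confirmed response.
4. State whether, for this analysis, a scan still at or below 50% of baseline but at least 25% above the smallest sum confirms the response. The confirmed rate depends materially on the answer.

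The cost is wording and a little more analysis, because the MRIs are already scheduled (8 weeks later in year 1, 12 weeks in year 2). The confirmed rate will be biased low, and a response first seen at the last scan before the data cut will stay unconfirmed. The report should say both.

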3.4.2.2. Pathology Review

Pathology must be reviewed in the UCSF pathology department.

Obtaining tissue samples:

- The UCSF Neurosurgery Tissue Bank has a general consent that patients sign to authorize release of their samples from previous surgeries at outside institutions.
- Slides and tissue blocks, along with a path report, are sent to UCSF -- c/o one of the NeuroOnc study coordinators or directly to the Neurosurgery tissue bank manager (currently [name])

Preparation of tissue samples:

- Once received, samples are logged into the Pathology computer system and assigned an SF#.
- If H&E slides are not provided, the tissue bank manager (currently [name]) will prepare unstained slides from paraffin blocks.
- The unstained slides will be staining at the UCSF Core lab.

Review of tissue samples:

- Pathology Materials Required for Review:
 - A copy of the Pathology Reports and the Operative Reports.
 - A Protocol Specific Pathology Submission Form.
- A neuropathologist () will review all H&E slides and will determine if the histology corresponds to the report and if it is adequate / appropriate for the study.
- The neuropathologist will also choose the blocks from which to prepare unstained slides for additional analysis.
- In general, one to two representative H&E stained slides from a pre-registration biopsy and when available from the original surgery will be reviewed.

Immunohistochemical assays:

All antigens to be assayed in this protocol are cytoplasmic or membranous and will be scored using a semi-quantitative scale as described herein:

To examine whether the *PTEN* promoter is methylated in glioma specimens, we will use methylation-specific primers that had previously been used to demonstrate methylation of the *PTEN* promoter in a subset of non-small-cell-lung cancer samples. These primers amplify a 181 base pair region of the *PTEN* promoter that starts 2477 nucleotides from the translation start site. The methylation-specific PCR (MSP) assay is sensitive to approximately 5% methylated product.

The designated neuropathologists will identify areas on the glass slide that are appropriately stained with the antibody, and will review the positive and negative control samples. The neuropathologist will then determine the ratio of tumor cells staining positive to those staining negative for the particular antibody. This interpretation does not consider intensity of staining per cell, but defines as "positive" all cells staining in a similar fashion to positive control cells. Based on this interpretation, the results are categorized into four groups:

- 0- negative staining = no staining in any of the tumor cells
- 1- focal positive staining = staining similar to positive control in less than one quarter of the tumor cells as determined by review of the entire slide and visual estimate.
- 2- Intermediate positive staining = staining similar to positive control in greater than one quarter but less than three quarters of tumor cells as determined by the review of the entire slide and visual estimate.
- 3- Diffuse positive staining = staining similar to positive control in greater than three quarters of the tumor cells as determined by the review of the entire slide and visual estimate.

Visual estimation may be aided by dividing the interpretable areas of the tissue on the slide into four quadrants using a tissue marker. It is beneficial to provide a visual scale in the form of a figure for the initial publications that will utilize the grading system. The results of this scoring can be reported as either a number representing each category, or descriptively using the terms negative, focal, intermediate, and diffuse.

Table 1: Summary of Assays to evaluate Phosphorylated Akt pathway

Molecular feature	Assay (reagents)
Phosphorylated PKB/Akt (phospho-PKB/Akt) expression	IHC: Polyclonal antibody Ser473; Cell Signaling Technology, Inc., Beverly, MA
PTEN promoter expression	IHC
Ribosomal S6 phosphorylation	IHC: phospho-specific antibody.
PRAS40	IHC

3.4.2.3 Radiology review

All objective responses must be reviewed by a neuro-oncologist at UCSF. Images will be viewed on the WebPACs system and comparison will be made between the most recent MRI image and the previous MRI image. Measurements and responses are judged based on criteria outlined in section 9.1. Discrepancies between measurements will be adjudicated by another neuro-oncologist at UCSF.

3.4.3 Safety assessments

Safety assessments will consist of monitoring and recording all adverse events and serious adverse events, the regular monitoring of hematology, blood chemistry and regular measurement of vital signs and the performance of physical examinations.

These assessments should be performed within ± 2 days of the scheduled day of assessment except for adverse events that will be evaluated continuously through the study. Safety and tolerability will be assessed according to the NIH/NCI CTC <http://ctep.cancer.gov/forms/CTCAEv3.pdf>.

3.4.3.1 Adverse events

Information about all adverse events, whether volunteered by the subject, discovered by investigator questioning, or detected through physical examination, laboratory test or other means, will be collected and recorded and followed as appropriate.

An adverse event is the appearance or worsening of any undesirable sign, symptom, or medical condition occurring after starting the study drug even if the event is not considered to be related to study drug. Medical conditions/diseases present before starting study drug are only considered adverse events if they worsen after starting study drug. Abnormal laboratory values or test results constitute adverse events only if they induce clinical signs or symptoms, are considered clinically significant, or require therapy.

The occurrence of adverse events should be sought by non-directive questioning of the patient at each visit during the study. Adverse events also may be detected when they are volunteered by the patient during or between visits or through physical examination, laboratory test, or other assessments. As far as possible, each adverse event should be evaluated to determine:

1. the severity grade (mild, moderate, severe) or (grade 1-4)
2. its relationship to the study drug(s) (suspected/not suspected)
3. its duration (start and end dates or if continuing at final exam)
4. action taken (no action taken; study drug dosage adjusted/temporarily interrupted; study drug permanently discontinued due to this adverse event; concomitant medication taken; non-drug therapy given; hospitalization/prolonged hospitalization)
5. whether it constitutes a serious adverse event (SAE)

All adverse events should be treated appropriately. Such treatment may include changes in study drug treatment including possible interruption or discontinuation, starting or stopping concomitant treatments, changes in the frequency or nature of assessments, hospitalization, or any other medically required intervention. Once an adverse event is detected, it should be followed until its resolution, and assessment should be made at each visit (or more frequently, if necessary) of any changes in severity, the suspected relationship to the study drug, the interventions required to treat it, and the outcome.

Information about common side effects already known about the investigational drug can be found in the [Investigators' Brochure]. This information should be included in the patient informed consent and should be discussed with the patient during the study as needed.

